#### **3.2 Study Endpoints**

#### 3.2.1 Primary efficacy endpoint

The primary efficacy objective of the study is to evaluate the effect of Opaganib on total supplemental oxygen requirement (area under the curve) using daily oxygen flow (L/min) measurements for 14 days (Day 1 to Day 14).

The primary efficacy endpoint will calculate for each patient the area under the curve of the supplemental oxygen requirement through day 14, using the trapezoidal rule after subtracting the baseline oxygen requirement at each day.

The following rules will be applied:

- If several values of oxygen requirement (L/min) are recorded in a certain day, then for the primary analysis the highest of these values will be taken.
- Days where no supplementary oxygen was needed, will be recorded as 0.
- Subjects who require intubation and mechanical ventilation, at these days will be assigned the maximal supplemental oxygen flow requirement of 8L/min (or if higher, the maximal value observed in the study).
- For subjects discharged from hospital without requiring supplemental oxygen prior to Day 14, the oxygen requirement (L/min) will be assigned thereafter as 0 for each day to Day 14 (in the rare case that subject will re-hospitalize before Day 14, the new supplemental oxygen data will be collected and used, until day 14).
- For the primary analysis, if a patient dies any time before Day 14), all his/her values (D1-D14) will be assigned at the maximal supplemental oxygen flow requirement of 8L/min, or if higher, the maximal value observed in the study.

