#### **3.2.2** Secondary Efficacy Endpoints

The secondary efficacy endpoints are as follows:

1. Time to 50% reduction from baseline in supplemental oxygen based on oxygen flow in L/min

This endpoint will be based on the oxygen flow values used for the primary efficacy endpoint. It will be calculated as the number of days from baseline (Day 1) of study

Statistical Analysis Plan	RedHill Biopharma
Version: 3, Date: 13-DEC-2020	Study ABC-110

medication until the first day when the subject reached a value, which is at least 50% lower than the baseline value (the event of interest). Patients who early terminate the study before reaching this reduction will have their time censored at the last valid observation time point. Patients who will die within the followup timeframe will be censored at the time of the end of the follow-up period, thus taking the highly unfavorable possible outcome for this endpoint. The time frame for this endpoint is from Day 1 until end of off-study-drug followup. Additional analysis will be performed in the time frame of the 14-day-treatment DB Phase period (sensitivity analysis).

To note, in order to focus this endpoint on sustained success, it implies increase in supplemental oxygen negating initial success would be followed for re-achievement of success. Further note, a patient who reached success but did not have any further data supporting this success (i.e. discharged from hospital still requiring oxygen and no further data supporting success afterwards), may be subject to sensitivity analysis where regarded censored at last evaluable time.

2. The percentage of patients no longer receiving supplemental oxygen for at least 24 hours by Day 14

This endpoint will be defined per subject as a binary ("Success" / "Failure") variable with "Success" indicating that a subject no longer receiving supplemental oxygen for at least 24 hours by Day 14, and "Failure" otherwise. Patients who will die within 14-days will be regarded as "Failure", corresponding to the highly unfavorable possible outcome.

To note, in order to focus this endpoint on sustained success, it implies need in supplemental oxygen negating initial success would be followed for re-achievement of success.

3. The time to two consecutive negative swabs for SARS-CoV-2 by PCR, at least 24 hours apart

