This time to event endpoint will be calculated as the number of days from baseline (Day 1 of study medication) until the earliest date of a reported requirement of intubation and mechanical ventilation, or death. Subjects who early terminate the study alive and without such requirement will have their time censored at the last valid observation time point. The time frame for this endpoint is from Day 1 until Day 30 from first dose. Additional analysis will be performed in the time frame of the 14-day-treatment DB Phase period (sensitivity analysis).

 The percentage of patients with at least one measurement of fever at baseline (defined as temperature >38.0 C[100.4 F]), who are afebrile (defined as temperature <37.2C [99 F]) at Day 14

This endpoint will be defined per subject as a binary ("Success" / "Failure") variable with "Success" indicating that a subject with fever at baseline is reported as afebrile on Day 14. "Failure" will be assigned otherwise.

This endpoint will be calculated only to the population of subject having fever at baseline. Additionally, to address objective # 3 (To evaluate the proportion of afebrile patients at Day 14), endpoint and analysis will be applied to the entire mITT analysis set.

8. Mortality due to any cause at Day 30.

This binary endpoint will be defined per subject as a binary ("Failure" / "Success") variable with "Failure" indicating that a subject had died within 30 days from first dose. "Success" will be assigned for patients known alive at day 30.

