### 5.4 Handling Withdrawals and Missing Data

Missing data in the primary endpoint are handled as described in sections 3.2.1 and 7.2. Sections 3.2.2 and 7.3 provides details on handling missing data for the secondary efficacy endpoints. Generally, no imputation will be performed for safety endpoints unless stated otherwise in the specific endpoint analysis. For time to event analysis, early withdrawal (or death before event of interest) will be addressed via right censoring, as described in Sections 3.2.2.

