This time to event endpoint will be analyzed using the same methods specified for the first secondary efficacy endpoint (without adjustment for the supplemental oxygen at baseline).

5. The percentage of patients requiring intubation and mechanical ventilation

This binary endpoint will be analyzed using the same methods specified for the second secondary efficacy endpoint. The event of interest is defined as "Failure". As defined in section 3.2.2. death will be analyzed as "Failure".

The percentage of patients requiring intubation and mechanical ventilation by Day 14 will be analyzed similarly.

6. The time to intubation and mechanical ventilation.

This time to event endpoint will be analyzed using the same methods specified for the 1st secondary efficacy endpoint (without adjustment for the supplemental oxygen at baseline).

 The percentage of patients with at least one measurement of fever at baseline (defined as temperature >38.0 C[100.4 F]), who are afebrile (defined as temperature <37.2C [99 F]) at Day 14

This binary endpoint will be analyzed using the same methods specified for the second secondary efficacy endpoint. This analysis will be based on observed case analysis using patients with Day 14 measurement.

8. Mortality due to any cause at Day 30.

This binary endpoint will be analyzed using the same methods specified for the second secondary efficacy endpoint. The event of interest is defined as "Failure". To note, in case that loss to follow up, the associated time to event analysis to derive the 30-days mortality rate will not encounter any competing event. Kaplan Meier curves of time to death through Day 30 will also be provided.

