### 10 SUMMARY OF CHANGES FROM LAST SAP VERSION AND PROTOCOL SPECIFIED ANALYSES

Version 2 of the SAP incorporates edits to the previous version of the SAP and some deviations in text from the latest version of the Clinical Study Protocol.

These edits/deviations, however, were made in response to the FDA recommendations, and attempts to insert greater detail and provide further clarifications. The most significant changes made to the text in this document are summarized in the table below:

Торіс	Change description and rationale	
Analysis	Per-protocol population was defined to address major protocol	
Populations	deviations that may occur, mainly relating to inclusion/exclusion criteria	
Primary efficacy	In Section 3.2.1: Originally, it was thought that multiple units will be used for reporting oxygen flow, and thus a placeholder for algorithm to	
endpoint and	address that was given. Yet, it was confirmed that all oxygen flow values	
analysis	will be reported using the same, L/min unit, therefore referral for further	
	addendum is no longer needed.	
	Imputation rules have been edited as follows:	
	
 
Following FDA recommendation, any death during study will be imputed using maximal supplemental oxygen flow requirement of 8L/min from Day 1 to Day 14 for the primary efficacy endpoint.
 
In case that higher values than 8L/min will be recorded, the SAP now define that 8L/min or if higher, the maximal value observed in the study will be used.
 
The SAP now address the scenario that a patient initiates new investigational therapy for COVID-19 within 14 days, in which case the primary analysis will include only measurement taken under study treatment and the rest of the days will be imputed according to imputation rules.
 
	
	In the sensitivity analysis (section 7.2.1.1): it was clarified that Change	
	from baseline will be analyzed in the model.	
	A supportive per-protocol analysis was added.	
Secondary	Following FDA recommendation and in accordance with the newly	
Efficacy	released COVID-19 guidance to address death as the highly unfavorable	
Endpoints	possible outcome for efficacy endpoints, the secondary endpoints and	
#1,#2,#5	associated analyses have been updated accordingly.	

 Table 2: Summary of changes in Version 2

Торіс	Change description and rationale
Secondary	The endpoint was changed based on FDA recommendation, and analysis
Efficacy	was subsequently fitted to analyze the resulting time to event endpoint.
endpoint #4	

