Secondary Efficacy	Clarification that analysis of this endpoint will be based on
endpoint #7 (Section	observed case analysis using patients with Day 14 measurement.
7.3)	
Safety analysis	A note on addressing case of patients who may have received a
general (Section 8.1)	flipped treatment due to bottle switches.
	**

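### Afebrile at Day 14 (secondary endpoint 7): SAP 3.2.2 and 7.3 use different denominators, give no explicit death rule, and imply conflicting treatments of a patient who dies

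*SAP*

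**What the plan says.** **Definition.** SAP 3.2.2 makes endpoint 7 binary. Success means that a patient with fever at baseline is "reported as afebrile on Day 14. 'Failure' will be assigned otherwise". No exception is made for a missing reading, and death is not mentioned. For objective 3 the same "endpoint and analysis will be applied to the entire mITT analysis set".

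**Analysis.** SAP 7.3 takes over the methods of secondary endpoint 2 and then adds: "This analysis will be based on observed case analysis using patients with Day 14 measurement". The endpoint 2 methods include a Kaplan-Meier estimate, used if loss to follow-up before the event is recorded, in which deaths are censored on Day 14.

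**Missing data.** SAP 5.4 states: "Sections 3.2.2 and 7.3 provides details on handling missing data for the secondary efficacy endpoints". It does not say which prevails.

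**History.** In SAP section 10, the version 3 table describes the 7.3 sentence as a "Clarification that analysis of this endpoint will be based on" observed cases, so the choice was deliberate. The version 2 table follows an FDA recommendation and the newly "released COVID-19 guidance to address death as the highly unfavorable" outcome for efficacy endpoints, but lists only secondary endpoints 1, 2 and 5 as updated.

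**Collection of temperature.** SAP Table 1 schedules vital signs on Day 14. Its first footnote makes the daily readings conditional on the patient being in hospital. SAP 5.5 moves an early-termination reading to the nearest scheduled day when that day's data are missing.

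**The concern.** A patient without a Day 14 temperature is a Failure under one section and absent under the other. Two programmers could produce different denominators and each cite the SAP.

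The patients affected are not a random sample. Those who die before Day 14 generally have no reading, so observed case conditions the comparison on survival. If deaths differ between arms, the difference in afebrile percentages is distorted, and the direction depends on which arm has more deaths. Patients discharged alive before Day 14 may also lack a reading, and many of them will have recovered. Scoring them as Failure, as 3.2.2 literally requires, raises the opposite problem.

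SAP 5.3 plans no formal hypotheses and reads the study by its overall pattern of benefits. The direction of each estimate is therefore what a reader will use.

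**Working it through.** The documents give no expected rate, effect size or death rate for this endpoint, so there is no stated figure to reproduce. The check compares the texts and then uses assumed counts.

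**1. The same patient under each text**

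| Patient | 3.2.2 | 7.3, observed case | Endpoint 2 fallback imported by 7.3 |
|---|---|---|---|
| Died before Day 14 | Failure | Excluded (unless 5.5 maps an early-termination reading to Day 14) | Censored on Day 14 |
| Alive, no Day 14 reading | Failure | Excluded | Censored at last observation if lost to follow-up |
| Measured, not afebrile | Failure | Failure | No event |
| Measured, afebrile | Success | Success | Event |

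The third column applies only if loss to follow-up is recorded. A death held at risk until Day 14 counts there much like a Failure. However, the method was written for an event occurring by Day 14, and endpoint 7 is a status on Day 14.

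**2. How death is handled elsewhere in the SAP.** In the primary endpoint (3.2.1), "if a patient dies any time before Day 14), all his/her values (D1-D14) will be assigned at the maximal supplemental oxygen flow requirement". In 3.2.2, endpoints 1 and 3 censor deaths at the end of follow-up as the unfavourable outcome, and endpoint 4 is defined like endpoint 3. Endpoints 2 and 5 score death as Failure, endpoint 6 counts it as an event, and endpoint 8 is death. Endpoint 7 is the one definition in 3.2.2 that neither mentions death nor adopts a definition that does.

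**3. Effect of deaths, assumed counts.** Input from the documents: 20 per arm (SAP 3.3). Death and afebrile counts are assumptions. Opaganib is listed first. Intervals are 95% Newcombe, built from Wilson limits.

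*More deaths on opaganib: 2 v 0 deaths, 14 v 15 afebrile.*
- Observed case: 14/18 = 77.8% v 15/20 = 75.0%, difference +2.8 points (-24.0 to 28.3).
- Death as Failure: 14/20 = 70.0% v 15/20 = 75.0%, difference -5.0 points (-30.9 to 21.8).

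*More deaths on placebo: 1 v 4 deaths, 18 v 15 afebrile.*
- Observed case: 18/19 = 94.7% v 15/16 = 93.8%, difference +1.0 point (-19.1 to 23.5).
- Death as Failure: 18/20 = 90.0% v 15/20 = 75.0%, difference +15.0 points (-9.4 to 38.0).

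**4. General size.** If both arms have afebrile rate q among survivors, the observed-case difference is 0. With k excess deaths in one arm of n, the all-patient difference against that arm is q × k / n. For n = 20 and q from 0.6 to 0.9:
- k = 1: 3.0 to 4.5 points
- k = 2: 6.0 to 9.0 points
- k = 3: 9.0 to 13.5 points

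**5. How often the sign changes.** I enumerated all integer outcomes with 0 to 4 deaths in one arm and k more in the other. I counted those where the arm with more deaths has the higher observed-case rate but fewer afebrile patients.

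| Excess deaths k | 20 per arm | 10 per arm (assumed size of fever subset) |
|---|---|---|
| 1 | 0 of 1720 | 0 of 370 |
| 2 | 41 of 1625 (2.5%) | 16 of 325 (4.9%) |
| 3 | 79 of 1530 (5.2%) | 28 of 280 (10.0%) |

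These are shares of an unweighted grid, not probabilities.

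**6. Living patients without a reading, assumed counts.** Take 1 v 1 deaths, 8 v 4 discharged alive without a reading, and 10 v 14 afebrile.
- Literal 3.2.2: 10/20 v 14/20, -20.0 points (-45.3 to 9.7).
- Observed case: 10/11 v 14/15, -2.4 points (-31.6 to 21.9).
- Death as Failure with observed case for the living: 10/12 = 83.3% v 14/16 = 87.5%, -4.2 points.

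Here most of the gap between the two SAP rules comes from discharged patients, so death and absence of a reading need separate rules.

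**The case against.** **7.3 can be read as settling the matter.** Sections 7.1 and 7.3 use mITT unless noted otherwise for a specific endpoint. The observed-case sentence is such a note, and the change log calls it a clarification. On that reading 3.2.2 codes the variable, 7.3 says who is analysed, and most analysts would follow 7.3. This is reasonable, but 3.2.2 was not narrowed to match. The planned summaries 14.2.8 and 14.2.9 still name the mITT sets, though section 12 presents that list as foreseen at study onset. Even if 7.3 governs, the conditioning on survival remains.

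**A reader might infer that endpoint 7 has no provision for death at all.** The documents do not support that. The default in 3.2.2 makes a death a Failure, and the endpoint 2 methods imported by 7.3 contain a death-censoring provision. What is missing is an explicit rule.

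**Temperature after death is undefined, so observed case is a legitimate choice.** This is fair for living patients. For deaths it departs, without a stated reason, from the principle in the SAP's own version 2 table.

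**Deaths are visible elsewhere.** Endpoint 8 reports mortality with Kaplan-Meier curves, endpoints 2 and 5 count death as Failure, and listing 16.2.12 gives derivations by subject. This limits the harm but does not decide the denominator.

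**The number affected may be small.** Day 14 is a scheduled visit, and Protocol 10.3 keeps patients who stop drug but stay in the study on the schedule. The number of living patients without a reading is unknown.

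**Conclusion.** The conflict between 3.2.2 and 7.3 stands, and so does the lack of an explicit death rule. Following 7.3 restricts the comparison to patients alive with a reading. With 20 per arm and equal afebrile rates of 60% to 90% among survivors, this hides 3.0 to 4.5 points per excess death.

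Two stronger readings are not supported. The bias does not favour opaganib by construction: it can hide a deficit or a benefit, depending on which arm has more deaths. Nor would an inference be overturned. No formal inference is planned, every interval computed above includes 0, and sign reversal is uncommon on the grid and absent with one excess death.

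The textual finding needs no assumption. The sizes rest on assumed deaths, afebrile counts and missing readings, since the documents give none. The change should be made, at low priority: the endpoint is secondary and mortality is reported separately.

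**What to change.** Align SAP 3.2.2 and 7.3, for both the fever-at-baseline subset and the whole mITT set:

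1. Count death on or before Day 14 as Failure and keep it in the denominator. State that this overrides any early-termination reading mapped under 5.5 and the death-censoring fallback imported from endpoint 2.
2. Keep observed case for patients alive without a Day 14 temperature, with missing-as-Failure as a sensitivity analysis.
3. Report by arm the numbers dead, alive without a reading (including those discharged), and measured.

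If the SAP is already final, document the change in the clinical study report, as the SAP preface provides.

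The cost is wording in two sections, a sensitivity analysis, and a set of counts in the endpoint 7 summaries. No new data are needed. The small downside is that the result for living patients without a reading depends on the rule chosen, which the sensitivity analysis will show.

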#### 7.4 Exploratory Endpoint analysis

The systemic markers of inflammation (D-dimer, cardiac troponin, C-reactive protein [CRP], lactate dehydrogenase [LDH] and ferritin) will be collected at Screening visit and then once weekly at Day 7 and Day 14 visits. These tests will be evaluated versus local site

normal ranges and assessed by the investigator as Clinically Significant (Yes/No). Changes from baseline analysis and other analyses similar to those planned for the Chemistry/Hematology laboratory tests (section 8.4) will be applied.

#### 7.5 Subgroup analysis

The primary and secondary endpoints will be summarized using the low vs. high oxygen flow subgroup as defined on section 5.6 above. The efficacy primary endpoint and 'Time to event' secondary endpoints will be analyzed by subgroup using the methods described in Section 7. Safety analysis may be provided as well, as deemed relevant.

### 8 SAFETY ANALYSIS

### 8.1 General

The safety population will be used for all safety analyses. Summaries will be presented by treatment group as actually received unless otherwise specified.

Rules to address safety data analysis of single patient who may have received a flipped treatment due to bottle switches are documented in study files, in which if the patient was initially on placebo but then mistakenly received opaganib, his/her data before and after the switch will be assigned as Placebo and opaganib, respectively, and thus may be counted twice.

### 8.2 Study Drug Administration

#### 8.2.1 Exposure to study drug

The following information will be summarized by treatment group:

- Duration of treatment (days treated) will be calculated as the number of days on treatment based on the first and last days of treatment with the study drug (last day of study drug first day of study drug + 1). Duration of treatment (days) will be summarized using appropriate descriptive statistics for continuous variable (section 5.1 above).
- Days on treatment will also be categorized as ≤10days or >10days and will be summarized using counts and percentages.
- The number and proportion of subjects with at least one dose reduction, and the total number of dose reduction will be tabulated.

#### 8.2.2 Treatment Compliance

Compliance with the prescribed study treatment will be assessed per subject, continuously from treatment initiation to end of treatment. The drug accountability log of returned study bottles will be used to evaluate the number of capsules used, unused and lost (recorded by site personnel). In addition, the Dose Missed/Reduced Log, which captures on a daily basis all missed or modified doses and reasons for modification, will be used to more accurately assess compliance.

Compliance rates will be presented as percentages, and subject-level compliance rates will be computed as follows: ([actual number of twice-daily doses taken]  $\div$  [expected number of twice-daily doses taken]) x 100.

Compliance rates will be summarized using appropriate descriptive statistics for continuous variable (section 5.1 above).

Compliance will also be categorized as  $\leq 80\%$  or >80% and will be summarized using counts and percentages.

Subject-level compliance details will be presented in a single data listing, incorporating count of dispensed (28 capsules) and returned capsules, number of expected vs. actual doses taken, occurrence of and reasons for missed and reduced doses, and computed compliance rates.

### 8.3 Adverse Events

All adverse events (AEs) will be coded using the Medical Dictionary for Regulatory Activities (MedDRA). Adverse events will be graded according to the revised NCI Common Terminology Criteria for Adverse Events (NCI-CTCAE version 5.0). If an AE is not listed in the NCI-CTCAE v.5.0, then the Physician will use the terms: mild/Grade 1, moderate/Grade 2, severe/grade 3, life-threatening/Grade 4, or death/Grade 5 to describe the maximum intensity of the AE, as specified in the protocol (section 15.2).

Only Treatment Emergent Adverse Events (TEAEs) will be summarized. TEAEs are defined as all AEs that start on or after the date of first dose.

The following summaries will be provided:

- An overall summary that will include the number and percentage of subjects with:
  - any TEAEs; any serious TEAE (TESAE);
  - any grade 3 or above TEAE; any grade 3 or above TESAE;
  - any treatment related (treatment related is defined as Possibly, Probably and related) related TEAEs, also missing relationship will be regarded as treatment related); any treatment related TESAE;
  - any treatment related TEAE grade 3 or above;
  - o any TEAE resulting in dose reduced; any TEAE resulting in drug withdrawn
  - any TEAE with an outcome of death
- Summaries by System Organ Class (SOC) and by Preferred Term (PT) within SOC will present the number and percentages of patients: experiencing any TEAEs; any TESAE; any grade 3 or above TEAE; any grade 3 or above TESAE; any treatment related TEAE; any treatment related TEAE; any TEAE resulting in dose reduced; any TEAE resulting in drug withdrawn; any AE with an outcome of death.
- Summary of TEAEs by SOC and PT and by maximum severity
- Summary of TEAEs by SOC and PT by maximal Relationship to Treatment

In summaries by SOC and PT, subjects are counted only once in each SOC category, and only once in each preferred term category.

In addition, characteristics of all TEAEs and TESAEs for all subjects will be presented in detail across multiple subject-level data listings. All AEs will be listed, regardless of whether they were treatment emergent. Listings for deaths, serious adverse events, adverse events leading to treatment withdrawal.

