## 15.1 Assessment of Casual Relationship

The following categories and definitions for assessing the causal relationship of an event to the investigational product(s) are provided as a guide to be used for evaluating adverse events reported in this study to determine "suspected adverse reactions" that require expedited reported to regulatory agencies if they are unexpected. In addition to the assessment below, the aggregate number of occurrences will be considered to decide whether the event is a reportable event and requires an IND safety report.

Table 2. Relationship of Study Medication to Adverse Events

Unrelated	The study drug elmost cortainly (or cortainly) did not cause the event		
Omerated	The study drug almost certainly (or certainly) did not cause the event.		
	Guidelines:  There is no reasonable temporal relationship of the event to the administration of drug:		
	There is no reasonable temporal relationship of the event to the administration of drug;		
	The pattern is inconsistent with that known for the drug; and/or		
	There is another obvious etiology.		
Probably	It is more likely that the event is due to another etiology than due to the study drug.		
not related	Guidelines:		
	There is no reasonable temporal relationship of the event to the administration of drug;		
	The pattern is inconsistent with that known for the drug; and/or		
	There is another more likely etiology.		
Possibly related	It is approximately equally likely that the event is due to the study drug as it is due to another etiology. Guidelines:		
	There is a reasonable temporal relationship of the event to the study drug;		
	The drug seems as likely as other etiologies to have caused the effect		
Probably	It is more likely that the event is due to the study drug than due to another etiology.		
related	Guidelines:		
	There is a reasonable temporal relationship of the event to the study drug;		
	The event may be consistent with a known pattern of drug (or drug class) effects;		
	The drug seems more likely than other etiologies to cause the effect;		
	The adverse event diminished upon cessation of study drug exposure or reduction in dose; and/or		
	The adverse event worsened or recurred upon unintentional re-exposure to the study drug (Intentional rechallenge for the purpose of assigning causality should not be performed.)		
Definitely	The evidence is compelling that the study drug caused the adverse event.		
related	Guidelines:		

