	There is a reasonable temporal relationship of the event to the study drug;		
	The event is consistent with a known pattern of drug (or drug class) effects;		
	The drug is far more likely than other etiologies to have caused the effect;		
	The adverse event diminished upon cessation of study drug exposure or reduction in dose;		
	The adverse event worsened or recurred upon unintentional re-exposure to the study drug (Intentional rechallenge for the purpose of assigning causality should not be performed.)		
Unknown	The data are inadequate to assign any of the above causal relationship categories to the study drug.		

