#### **1 PREFACE**

This Statistical Analysis Plan (SAP) describes the planned analysis and reporting for RedHill Biopharma Ltd. study ABC-110 (Opaganib, a Sphingosine Kinase-2 (SK2) Inhibitor in COVID-19 Pneumonia: a Randomized, Double-blind, Placebo-Controlled Phase 2a Study, in Adult Subjects Hospitalized with SARS-CoV-2 Positive Pneumonia), and was written in accordance with SOP 100-60-02 (Statistical Analysis Plan Preparation, Review and Approval, Bioforum's Procedure).

The structure and content of this SAP provides sufficient detail to meet the requirements identified by the FDA and International Conference on Harmonization of Technical Requirements for Registration of Pharmaceuticals for Human Use (ICH): E9 Guidance on Statistical Principles in Clinical Trials. All work planned and reported for this SAP will follow internationally accepted guidelines, published by the American Statistical Association, and the Royal Statistical Society, for statistical practice.

The following documents were reviewed in preparation of this SAP:

- Clinical Study Protocol ABC-110, version 1.2,30 August 2020.
- Case report forms (CRFs) for Study ABC-110.
- ICH E9 Guidance on Statistical Principles for Clinical Trials.
- ICH E3 Structure and Content of Clinical Study Reports
- COVID-19: Developing Drugs and Biological Products for Treatment or Prevention Guidance for Industry, May 2020.
- Statistical Considerations for Clinical Trials During the COVID-19 Public Health Emergency, Guidance for Industry, June 2020

The reader of this SAP is encouraged to also read the clinical protocol for details on the conduct of this study, and the operational aspects of clinical assessments and timing for completing a patient in this study. When differences exist in descriptions or explanations provided in the protocol and this SAP, the SAP prevails. Any deviations from the statistical analyses planned in the protocol will be documented in the SAP and any deviations from the statistical analyses planned in the SAP will be documented in the final clinical study report (CSR).

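### SAP 8.3 counts a blank causality field as treatment related but, read literally, leaves out events recorded under the protocol's Unknown category

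*SAP*

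**What the plan says.** SAP 8.3 (Adverse Events) sets the rule for the treatment-related summaries: "treatment related is defined as Possibly, Probably and related". The same parenthesis continues: "also missing relationship will be regarded as treatment related". The definition is used in the overall summary (related TEAEs, related serious TEAEs, related TEAEs of grade 3 or above) and in the tables of related events by SOC and PT. In SAP section 12 these are Tables 14.3.2.1, 14.3.2.6 and 14.3.2.7. SAP 8.3 also plans a "Summary of TEAEs by SOC and PT by maximal Relationship to Treatment", which is Table 14.3.2.12.

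Protocol 15.1, Table 2, gives the investigator six categories: Unrelated, Probably not related, Possibly related, Probably related, Definitely related and Unknown. The last is defined as "The data are inadequate to assign any of the above causal relationship categories to the study drug".

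The SAP does not mention *Unknown* causality in 8.3 or anywhere else. On precedence, SAP section 1 says: "When differences exist in descriptions or explanations provided in the protocol and this SAP, the SAP prevails".

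**The concern.** For events with no causality entry the SAP has chosen a conservative rule: count them as related. An investigator who records *Unknown* reports the same absence of information, but has written it down. The definition as worded treats the two differently. A site that leaves the field empty produces a related event; a site that documents that causality could not be judged does not.

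Safety and tolerability is a stated objective (SAP 2.4), and attribution can be difficult in this trial. Two of the events of special interest in SAP 8.3.1, a sudden rise in oxygen requirement and a decline leading to intubation, can be caused by the disease itself. For the neuropsychiatric events on the same list, Protocol 6.4.1.2 reports that every affected patient in the myeloma study was also taking narcotic analgesics. *Unknown* is therefore a plausible entry, although no document says how often it is used.

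The rule can also be programmed in two ways. One programmer may read missing relationship as including *Unknown* and another may not, and the same data would then give different tables.

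**Working it through.** The plan gives no figure to reproduce. The check maps each Table 2 category onto the SAP 8.3 definition.

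**Step 1. Mapping.**

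| Causality record | Protocol 15.1 meaning | Under SAP 8.3 |
|---|---|---|
| Unrelated | drug almost certainly not the cause | not counted |
| Probably not related | "It is more likely that the event is due to another etiology than due to the study drug" | not counted |
| Possibly related | "It is approximately equally likely that the event is due to the study drug as it is due to another etiology" | counted |
| Probably related | drug the more likely cause | counted |
| Definitely related | "The evidence is compelling that the study drug caused the adverse event" | counted, if this is what the SAP calls *related* |
| Unknown | "The data are inadequate to assign any of the above causal relationship categories to the study drug" | not listed and not missing, so not counted by default |
| Field left empty | no entry | counted, by explicit rule |

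The last two rows are the inconsistency: equal information, opposite result.

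**Step 2. Does another part of the plan settle it?** No. The protocol defines *Unknown* but does not say which side of a related/not-related split it belongs to, so it does not resolve the SAP's silence. The precedence clause in SAP section 1 makes the SAP wording the operative one. The nearest analogue points toward inclusion: SAP 8.10 treats a medication as concomitant when its dates do not allow a decision.

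**Step 3. The maximal-relationship table.** Table 14.3.2.12 needs an order of categories. If a subject has one *Unknown* and one *Probably not related* event under the same PT, no rule says which is the maximum.

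**Step 4. Size.** The planned arm size is 20 (SAP 3.3). Let k be the number of subjects in an arm whose only candidate related event is recorded as *Unknown*. Counting rather than not counting *Unknown* changes that arm's related-event percentage by 100 × k / 20. The documents give no value for k, so a range is assumed:

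- k = 1: 100 × 1/20 = 5 points
- k = 2: 100 × 2/20 = 10 points
- k = 3: 100 × 3/20 = 15 points

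The change in the between-arm difference is 100 × (k in the opaganib arm − k in the placebo arm) / 20. With 2 against 0 it is +10 points, with 0 against 2 it is −10, and with equal numbers it is 0. The sign cannot be known in advance.

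**The case against.** The strongest reply is that the SAP is silent on *Unknown* rather than wrong. It assigns the category to neither side, and since the definition of *Unknown* describes inadequate data, reading it as a form of missing relationship is reasonable. The list itself is loosely worded: *related* is not a Table 2 label, and a strictly literal reader would have to exclude *Definitely related* too, which cannot be intended. On this view the list is shorthand and should not bear a strict-exclusion argument.

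Part of this stands. The exclusion follows from applying the definition as worded, and the SAP never states it. But *related* has an obvious counterpart in Table 2, and *Unknown* has none on the SAP list. If the broader reading of missing is intended, it should be written down, because the tables depend on it.

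A second reply is that Protocol 15.1 offers its categories only as a guide. The SAP was written after review of the CRFs (SAP section 1), and its labels differ from Table 2. If the eCRF does not offer *Unknown*, the gap has no effect. This stands as a condition on the whole point, since the eCRF is not among the documents.

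A third reply is that little depends on it. The events remain in the all-TEAE, serious and grade 3 or above tables and in the listings. Treatment is blinded, and SAP 5.3 rules out inferential reading of p-values. All of this stands and limits the severity.

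A fourth reply is that pooling *Unknown* with related is only one convention, and that it could raise both arms' rates and blur the contrast between them. This is fair, and it is why the category should also be shown separately.

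**Conclusion.** The point holds as a minor inconsistency. As worded, SAP 8.3 counts an empty causality field as treatment related and does not count a recorded *Unknown*, against its own conservative rule for absent causality. The effect is confined to the descriptive tables of related TEAEs, related serious TEAEs and related TEAEs of grade 3 or above, and to the undefined rank in Table 14.3.2.12. Each affected subject changes an arm's rate by 5 points; one to three such subjects would change it by 5 to 15 points.

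This rests on three assumptions: the eCRF offers *Unknown*, *Unknown* is not treated as missing in programming, and the arms are at their planned size of 20.

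A reader might infer two stronger claims that the documents do not support. The first is that the SAP classes these events as unrelated. It does not: they are left out of the related count by default, and no rule labels them unrelated. The second is that the rule understates opaganib's related-event rate relative to placebo. The omission can occur in either arm, causality is assessed under blinding, and no frequency of *Unknown* is given, so neither a shift in the difference nor its direction can be asserted.

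**What to change.** In SAP 8.3, replace the parenthesis with a definition that uses the Table 2 labels: treatment related means Possibly related, Probably related or Definitely related, Unknown, or missing. In the same place, state that Table 14.3.2.12 shows *Unknown* as its own category and give its rank for the maximal-relationship rule. Readers can then see how much of the related rate comes from events that could not be assessed. Check the wording against the causality options in the eCRF; if *Unknown* is not offered, say so and no further change is needed.

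The cost is one or two lines in the SAP and a small change to one table shell. The downside is that related-event rates may be somewhat higher in both arms, which the separate category makes visible. No sample size, efficacy analysis or data collection changes. If the first database lock has already passed, SAP section 1 requires the change to be documented in the clinical study report.
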